3.1 Background information

3.1.1 Haemophilia

Haemophilia is an inherited bleeding disorder characterised by an increased bleeding tendency, typically in weight bearing joints. Haemophilia A is caused by a partial or complete deficiency of blood coagulation factor VIII (FVIII) and haemophilia B is caused by defect factor IX (FIX). Inheritance is chromosome X-linked and recessive; therefore the disease mainly affects males. The incidence of haemophilia A and B on average is estimated to be about 1 in 5000 live male births⁴. According to the World Federation of Haemophilia global survey of 2014, about 178,500 persons are diagnosed with haemophilia worldwide. Of these, about 80% have haemophilia A.

Haemophilia is classified as “severe”, “moderate” or “mild” according to the plasma activity level of the affected coagulation factor⁵. With a deficiency of FVIII or FIX, the degree of activation of coagulation factor X (FX) becomes insufficient. Consequently, the thrombin burst is delayed and insufficient for normal haemostasis⁶. The haemostatic plug, if formed, in these patients is fragile and easily dissolved by normal fibrinolytic activity. This leads to impaired haemostasis and spontaneous prolonged bleeding episodes. In severe haemophilia, bleeding in joints occurs spontaneously and is the most frequent symptom of the disease. Recurrent bleeding episodes in the same location - most commonly a weight bearing joint - lead to chronic arthropathy, muscular atrophy and deformities. Treatment of bleeding episodes as they manifest (on-demand treatment) may delay arthropathy, but does not prevent it. The majority of children with severe haemophilia experience their first bleeding episode in a joint prior to the age of 4 years. Many children also bleed from other body sites, also before this age is reached⁷. For this reason, primary prophylaxis treatment with regular FVIII injections in the non-bleeding state is the recommended from early childhood.

The most common complication of replacement therapy is development of antibodies binding to FVIII. These binding antibodies might neutralise the exogenous of FVIII and are then called inhibitors. In patients who have developed inhibitors towards FVIII, replacement therapy is

Protocol
 Trial ID:NN7415-4255
 UTN:U1111-1179-3872
 EudraCT no.:2016-000614-29

~~CONFIDENTIAL~~

Date: 28 August 2018
 Version: 5.0
 Status: Final
 Page: 22 of 127

Novo Nordisk

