8.1.9.5 Visit 9 (Assessment visits)

Visit 9 is to be scheduled on trial day 169 (24 weeks) with a visit window of \pm 7days.

Treatment with concizumab must take place after the blood sampling at this visit.

Patients will be asked to complete the PRO questionnaires before any other trial related activities are performed according to section [8.6.1](#);

- PGI-C
- Hemo-TEM
- SF-36v2
- SDS
- TSQM
- H-DAT
- SIAQ-ISRQ

Assessments are to be performed according to [Table 2-1](#) and the assessment results from physical examination, concomitant medication, vital signs, Body measurements (weight only) and details of adverse events must be entered into the eCRF.

Investigator is to perform compliance check of treatment and reporting of bleeding episodes through the available access to collected data from the eDiary. Based on the assessment of any spontaneous bleeding episodes the investigator must evaluate if an escalation of the concizumab doses is needed according the escalation rules described in section [5.3.1](#). All decisions to escalate the concizumab dose must be recorded in the eCRF.

The patient will be asked to return all used, partly used and unused concizumab cartridges and turoctocog alfa (FVIII) during the trial as instructed by the investigator. Drug accountability must be performed at all visits for concizumab and rFVIII (turoctocog alfa) including injection kits, if applicable. Unused sodium chloride syringes should be returned to site at every visit and new sodium chloride syringes should be dispensed to the patient.

Protocol
 Trial ID:NN7415-4255
 UTN:U1111-1179-3872
 EudraCT no.:2016-000614-29

~~CONFIDENTIAL~~

Date:	28 August 2018	Novo Nordisk
Version:	5.0	
Status:	Final	
Page:	49 of 127	

In order to determine the correct amount of the patient's daily dose of concizumab, until next scheduled visit, investigator will consult the dosing-table in the TMM on basis of the patient's current body weight. Investigator will communicate any corrections in the daily dose of concizumab to the patient and record the dose for the coming home treatment period in the eCRF.

A dispensing call must be performed in the IWRS.

At the visit the patient will be provided with trial product (concizumab and if necessary rFVIII (turoctocog alfa)) and injection kits to be able to conduct home treatment until next scheduled visit.

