Prophylactic treatment with concizumab should continue independent of bleeding episodes and their treatment, i.e. the original dosing schedule should be maintained unless investigator judges otherwise. Decisions to alter dosing schedule, including the rationale for the alteration, should be documented. If applicable, investigator must instruct the patient to use rFVIII (turoctocog alfa) as rescue medication to treat bleeding episodes.

Treatment of bleeding episodes will be at the discretion of the investigator. In countries where turoctocog alfa is approved for the market it is recommended to follow the approved labelling for NovoEight[®]. For countries where turoctocog alfa is not approved it is recommended to follow the instructions in the EU-SMPC for turoctocog alfa (FVIII): “The calculation of the required dose of factor VIII is based on the empirical finding that 1 IU factor VIII per kg body weight raises the plasma factor VIII activity by 2 IU/dl. The required dose is determined using the following formula: Required units (IU) = body weight (kg) x desired factor VIII rise (%) (IU/dl) x 0.5 (IU/kg per IU/dl).

The amount to be administered and frequency of administration should always be oriented to the clinical effectiveness in the individual case.

Protocol
 Trial ID:NN7415-4255
 UTN:U1111-1179-3872
 EudraCT no.:2016-000614-29

~~CONFIDENTIAL~~

Date: 28 August 2018
 Version: 5.0
 Status: Final
 Page: 59 of 127

Novo Nordisk

In case of the following haemorrhagic events, the factor VIII activity should not fall below the given plasma activity level (in % of normal or IU/dl) in the corresponding period. The following table can be used to guide dosing in bleeding episodes and surgery:”

Table 8–4 Guide for dosing in bleeding episodes and surgery

Degree of haemorrhage/ Type of surgical procedure	FVIII level required (%)(IU/dl)*	Frequency of doses (hours)/ Duration of therapy (days)
Haemorrhage		
Early haemarthrosis, muscle bleeding or oral bleeding	20-40	Repeat every 12 to 24 hours, at least 1 day, until the bleeding episode as indicated by pain is resolved or healing achieved
More extensive haemarthrosis, muscle bleeding or haematoma	30-60	Repeat infusion every 12-24 hours for 3-4 days or more until pain and acute disability are resolved
Life threatening haemorrhages	60-100	Repeat infusion every 8 to 24 hours until threat is resolved
Surgery		
Minor surgery including tooth extraction	30-60	Every 24 hours, at least 1 day, until healing is achieved

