8.5.1 Laboratory assessments for efficacy

8.5.1.1 Thrombin generation

The Thrombin Generation Assay (TGA) will be performed at all visits (including unscheduled 24 hour PK visit), except visit 3.

The TGA is included as an exploratory PD assessment.

The generation of thrombin is a fundamental part of the haemostatic system, and is a key measurable parameter of the formation of a clot under bleeding or thrombotic conditions. The thrombin burst is crucial for the formation of a stable fibrin clot.

The Calibrated Automated Thrombogram (CAT) method (used by Thrombinoscope BV) will be used to measure thrombin generation (TG). This method uses a slow acting fluorogenic substrate that allows continuous measurement of thrombin generation in double centrifuged citrated plasma.

Protocol
 Trial ID:NN7415-4255
 UTN:U1111-1179-3872
 EudraCT no.:2016-000614-29

~~CONFIDENTIAL~~

Date:	28 August 2018	Novo Nordisk
Version:	5.0	
Status:	Final	
Page:	65 of 127	

In this assay set-up thrombin generation is initiated by low-dose tissue factor that is combined with phospholipid. The result is obtained by comparison to a constant known thrombin activity in a parallel non tissue factor initiated sample. The assay has been validated fit-for-purpose.

The thrombin generation endpoints are defined, but not limited to,

- The Endogenous Thrombin Potential (ETP) – the area under the curve
- Peak thrombin generation
- Velocity Index

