8.5.2.6 FVIII inhibitor test

The inhibitor level of the patient will be measured by the Nijmegen method at visit 1 (screening).

- FVIII inhibitor titre (BU)

In order to minimise the risk of false negative results, circulating FVIII product levels should be less than 0.05 IU/ml, when sampling for the test. If the patient has received FVIII within 96 hours of screening, the sampling of FVIII-Inhibitor should be postponed until a time period equal to 8 half-lives of the used product has passed (counting from latest treatment).

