17.5 Additional analyses

An additional evaluation of the primary endpoint will be made, including actual concizumab dose level (interpreted as the patient's last dose level) as *additional factor in the primary analysis model specified above*. Point estimates and 95% confidence interval will be provided for the ABR at the different dose levels of concizumab (0.15, 0.20 and 0.25 mg/kg). Furthermore, a series of analyses with individual steady state PK/PD assessments included as covariates in the negative binomial regression model as specified for the primary analysis will be performed in order to evaluate possible associations between PK/PD and ABR that potentially could guide dose-selection. The referred steady-state PK/PD assessments comprise the concizumab trough level, maximum plasma concentration (C_{max}) of concizumab, TFPI value prior to the last s.c. dose administration, peak thrombin generation (nM), Endogenous thrombin potential (nM*min) and velocity index (nM/min).

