17.6.4 Supportive secondary pharmacodynamic endpoints

Free TFPI concentration:

- Value prior to the last dose administration at 24 weeks.
- Value prior to the last dose administration after at least 76 weeks.

Thrombin generation:

- Peak thrombin generation (nM) prior to the last dose administration at 24 weeks.
- Peak thrombin generation (nM) prior to the last dose administration after at least 76 weeks.
- Endogenous thrombin potential (nM*min) prior to the last dose administration at 24 weeks.
- Endogenous thrombin potential (nM*min) prior to the last dose administration after at least 76 weeks.
- Velocity index (nM/min) prior to the last dose administration at 24 weeks.
- Velocity index (nM/min) prior to the last dose administration after at least 76 weeks.

The PD endpoints will be summarized and listed.

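### Section 17.5 regresses ABR on thrombin generation without handling samples drawn under rescue FVIII, so the bleeds being counted shift the covariate and pull the association toward zero

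*Protocol*

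**What the plan says.** Section 17.5 plans a series of negative binomial models with individual steady-state PK/PD values as covariates, in order to explore "possible associations between PK/PD and ABR that potentially could guide dose-selection". Three of the six covariates are thrombin generation measures: peak, ETP and velocity index. The other three are concizumab trough, Cmax and TFPI. Section 17.6.4 summarises the thrombin generation measures as secondary pharmacodynamic endpoints, for example "Peak thrombin generation (nM) prior to the last dose administration at 24 weeks".

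Section 8.5.1.1 sets the sampling: "The Thrombin Generation Assay (TGA) will be performed at all visits (including unscheduled 24 hour PK visit), except visit 3". On treatment, the timing rules concern the concizumab dose only. At visit 9, "Treatment with concizumab must take place after the blood sampling at this visit"; visit 16 and the 24-hour PK visit have similar rules. Rescue FVIII may be given for breakthrough bleeds throughout the trial (5.3.2). For the more extensive bleeds Table 8-4 says: "Repeat infusion every 12-24 hours for 3-4 days or more until pain and acute disability are resolved".

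Elsewhere the protocol does control FVIII carry-over: 48 hours before the first concizumab dose (8.1.9.1), 96 hours for screening FVIII activity when the baseline level is undocumented (8.1.7), and for the inhibitor test "circulating FVIII product levels should be less than 0.05 IU/ml, when sampling for the test" (8.5.2.6).

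**The concern.** Section 3.1.1 describes what lack of FVIII or FIX does: "Consequently, the thrombin burst is delayed and insufficient for normal haemostasis". The assay measures that burst in the patient's own plasma after a low-dose tissue factor trigger (8.5.1.1), so infused FVIII should raise the result. Section 17 counts treated bleeds only, so a counted bleed comes with treatment close to it in time. A patient who bleeds often is more likely to have FVIII on board when sampled, and his thrombin generation then reads higher because he bled.

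This is reverse causation. It works against the association the model looks for, in which more thrombin generation goes with less bleeding. At stake is whether the three thrombin generation models can be interpreted: a flat result could mean no relation, or a real one masked by rescue FVIII. The 24-week summaries in 17.6.4 would also credit some FVIII-driven thrombin generation to concizumab.

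**Working it through.** **Inputs from the protocol.** Section 17.1: 30 patients, ABR 4, over-dispersion 6, 6 months on average. Section 17: threshold 12, 95% confidence interval. FVIII intervals of 48 h and 96 h as above. A 4-day course (Table 8-4) plus 96 h gives 192 h.

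**Assumed, because the documents give no figure.** The shift in thrombin generation caused by FVIII (1-4 SD), how long it lasts, and the true slope of log bleeding rate per SD of thrombin generation.

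**1. The plan's own figure.** SE of the log rate = sqrt(6/(30 × 4 × 0.5)) = 0.316. Power = Φ(ln(12/4)/0.316 − 1.96) = Φ(1.51) = 93.5%. Simulating the negative binomial fit gives 95.6%, against the stated 95%. The planning model is therefore reproduced and is used below. The power itself is not affected by this point.

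**2. How often a sample is affected.** With random timing, P(treated bleed within h hours before a sample) = 1 − exp(−ABR × h/8766).

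| ABR | 48 h | 96 h | 192 h |
|---|---|---|---|
| 4 | 2.2% | 4.3% | 8.4% |
| 12 | 6.4% | 12.3% | 23.1% |
| 20 | 10.4% | 19.7% | 35.5% |

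At ABR 4 this is 0.043 × 30 = 1.3 to 0.084 × 30 = 2.5 affected samples per visit. They are few, but the chance rises with the outcome. Visits triggered by bleeding, such as the visit 9-type procedures soon after a stop for lack of efficacy (8.1.4), are not in these figures and would add to them.

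**3. Effect on the slope, constant shift.** 250 simulated trials per setting (30 patients, 0.5 years, ABR 4, over-dispersion 6). The covariate is raised by a fixed amount if a treated bleed fell inside the window before the sample. Cells show the median estimate and the share of trials with the wrong sign.

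| Window, shift | True slope −0.3 | True slope −0.7 |
|---|---|---|
| No contamination | −0.27 to −0.33 (17-26%) | −0.66 to −0.75 (2-5%) |
| 48 h, 1 SD | −0.21 (27%) | −0.59 (5%) |
| 96 h, 1 SD | −0.14 (36%) | −0.53 (9%) |
| 96 h, 2 SD | −0.05 (41%) | −0.34 (21%) |
| 96 h, 3 SD | +0.02 (52%) | −0.13 (36%) |
| 192 h, 3 SD | +0.15 (76%) | +0.03 (53%) |

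In every setting the median estimate is less negative than the true slope.

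**4. Constant against decaying shift.** A fixed shift over days ignores FVIII clearance. With 30 patients, 168 days, negative binomial dispersion 2 (variance/mean = 1 + 2 × 2.5 = 6 at a mean of 2.5 bleeds), a true slope of −0.5 and ABR 4-5:

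- constant shift of 1-4 SD for 4-8 days: −0.38 to +0.13;
- shift decaying with a 12 h half-life (assumed, reading 96 h as 8 half-lives, 96/8 = 12): −0.43 to −0.28. A second run with courses of 0-1 day gave −0.49 to −0.22, and the median never changed sign.

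**The case against.** The strongest objection is that excluding values from an additional analysis is data handling, which belongs in an analysis plan or laboratory manual not shown here. That stands as to where the detail may be written. It does not remove the point. The protocol itself names the covariates, their purpose and the sampling conditions, and it controls concizumab timing and, for other tests, FVIII carry-over. Followed as written, it lets the outcome move the covariate.

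Other points on that side stand:

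- The magnitude rests on an assumed FVIII effect, and under decay the bias is moderate.
- Section 17.5 names no visit for the thrombin generation covariate. The simulations use one last sample; an average over visits would be less affected.
- The models are exploratory and weak in any case. In a comparable simulation at mean ABR 5, a clean slope of −0.5 was detected in only 35% of trials.
- The 96-hour and 8-half-life rules were written for FVIII activity and inhibitor testing, not for thrombin generation, so 96 hours is an available convention and not a validated washout.

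A reader might also infer that the relation between concizumab exposure and bleeding is hidden or reversed. The documents do not support that. Exposure enters through trough and Cmax in their own models, and nothing in the protocol says that FVIII changes these or TFPI.

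**Conclusion.** The point holds for the three thrombin generation models in 17.5 and the thrombin generation summaries in 17.6.4. The expected result at the planned bleeding rates is attenuation: a true slope of −0.5 per SD is estimated at about −0.4 to −0.3 if the FVIII effect decays with a 12-hour half-life, and at about −0.4 to +0.1 if a constant 1-4 SD shift persists for 4-8 days.

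Reversal of sign should not be read as the likely outcome. It needs a large and long-lasting FVIII effect or much more frequent bleeding. Concizumab trough, Cmax, TFPI, the ABR estimates by dose level and both proof-of-concept criteria are untouched, so neither the main conclusion nor the dose guidance as a whole is put in doubt. The conclusion rests on FVIII raising the assay result, which follows from 3.1.1, and on an effect size that the documents do not state.

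**What to change.** In 17.5 and 17.6.4, use the FVIII dose dates and times already recorded under 8.3.1 to flag any thrombin generation value taken within a pre-specified interval after an FVIII dose. Ninety-six hours is one option, since the protocol already uses it for FVIII activity sampling. Exclude flagged values from the main thrombin generation models and summaries, list them, and repeat the analysis on all samples as a sensitivity analysis.

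Replace an excluded value only with another FVIII-free sample at the same dose level that is confirmed to precede that day's concizumab dose; otherwise treat it as missing. Values from visits 4-8 cannot be substituted freely, because patients then dose at home regardless of visit timing (8.1.9.4) while 17.6.4 calls for pre-dose values.

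The cost is a sentence in each section and a derived flag, with no new samples or visits. A few patients lose a value, about 1 to 3 of 30 at one visit at ABR 4. They will mainly be frequent bleeders, so the exclusion is itself related to outcome; this is why the all-samples analysis should be kept alongside.

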17.6 Secondary endpoints

17.6.1 Supportive secondary efficacy endpoints

- The number of bleeding episodes during at least 76 weeks from treatment onset.
- The number of spontaneous bleeding episodes during at least 24 weeks from treatment onset.
- The number of spontaneous bleeding episodes during at least 76 weeks from treatment onset.

The supportive secondary endpoints will be estimated using the same negative binomial regression model as the primary endpoint and performing the same two analyses as for the primary endpoint; one only including observations from the period on the last dose level and one including the entire escalation pattern.

Protocol
 Trial ID:NN7415-4255
 UTN:U1111-1179-3872
 EudraCT no.:2016-000614-29

~~CONFIDENTIAL~~

Date: 28 August 2018
 Version: 5.0
 Status: Final
 Page: 106 of 127

Novo Nordisk

17.6.2 Supportive secondary safety endpoints

- Number of treatment-emergent adverse events (TEAEs) during at least 24 weeks from treatment onset
- Number of TEAEs during at least 76 weeks from treatment onset
- Occurrence of anti-concizumab antibodies during at least 24 weeks from treatment onset
- Occurrence of anti-concizumab antibodies during at least 76 weeks from treatment onset
- Change from baseline of fibrinogen during 24 weeks from treatment onset
- Change from baseline of fibrinogen during at least 76 weeks from treatment onset
- Change from baseline of D-dimer during 24 weeks from treatment onset
- Change from baseline of D-dimer during at least 76 weeks from treatment onset
- Change from baseline of prothrombin fragment 1 + 2 (F1 + 2) during 24 weeks from treatment onset
- Change from baseline of F1 + 2 during at least 76 weeks from treatment onset
- Change from baseline of prothrombin time (PT) during 24 weeks from treatment onset
- Change from baseline of PT during at least 76 weeks from treatment onset
- Change from baseline of activated partial thromboplastin time (APTT) during 24 weeks from treatment onset
- Change from baseline of APTT during at least 76 weeks from treatment onset
- Change from baseline of anti-thrombin (AT) during 24 weeks from treatment onset
- Change from baseline of AT after at least 76 weeks from treatment onset

Adverse Events will be coded using the most recent version of Medical Dictionary for Regulatory Activities (MedDRA) coding.

A Treatment Emergent Adverse Event (TEAE) is defined as an event that has onset from the first exposure to treatment until the last visit in the trial. Adverse events collected among permanently prematurely discontinued from trial product due to a safety concern patients after visit 17 in the possible extended follow-up (ref section [8.1.4](#)) are not considered treatment emergent. Treatment-emergent adverse event endpoints will be summarised by system organ class, preferred term, seriousness, severity and relation to trial product. All Adverse events will further be listed.

Frequency of binding anti-concizumab antibodies will be listed and summarised by time frame according to the two endpoint definitions.

All laboratory safety endpoints will be plotted by time, both as absolute values and change from baseline. Laboratory safety endpoints will further be summarised and listed.

17.6.3 Supportive secondary pharmacokinetic endpoints

- Concentration of concizumab prior to the last dose administration at 24 weeks.
- Concentration of concizumab prior to the last dose administration after at least 76 weeks.

Protocol
Trial ID:NN7415-4255
UTN:U1111-1179-3872
EudraCT no.:2016-000614-29

~~CONFIDENTIAL~~

Date: 28 August 2018
Version: 5.0
Status: Final
Page: 107 of 127

Novo Nordisk

The pharmacokinetic endpoints will be summarised and listed.

17.6.4 Supportive secondary pharmacodynamic endpoints

Free TFPI concentration:

- Value prior to the last dose administration at 24 weeks.
- Value prior to the last dose administration after at least 76 weeks.

Thrombin generation:

- Peak thrombin generation (nM) prior to the last dose administration at 24 weeks.
- Peak thrombin generation (nM) prior to the last dose administration after at least 76 weeks.
- Endogenous thrombin potential (nM*min) prior to the last dose administration at 24 weeks.
- Endogenous thrombin potential (nM*min) prior to the last dose administration after at least 76 weeks.
- Velocity index (nM/min) prior to the last dose administration at 24 weeks.
- Velocity index (nM/min) prior to the last dose administration after at least 76 weeks.

The PD endpoints will be summarized and listed.

